#### **Abstract**

Raynaud's phenomenon (RP) is a common vascular disorder that affects approximately 10% of the general population. RP is associated with significant morbidity that may include loss of the digits due to repeated episodes of vasospasm of the digital arteries in addition to significant impairment of quality of life. It is well known that cold exposure precipitates episodes of RP, but the mechanism for cold sensitivity is not known, and treatment of RP is not satisfactory to the subjects and their physicians.

Our goal in this proposal is to test the possibility that non invasive vagus nerve stimulation (nVNS) with gammaCore may be an effective and well tolerated therapy for RP. We will perform the first proof of concept human study to demonstrate the clinical efficacy and safety of nVNS using gammaCore in RP.

We anticipate at the conclusion of the proposed work that we will have gained fundamental understanding of the role of nVNS as a potential therapy for RP, a truly unmet medical need. If successful in demonstrating measurable local vasodilatory effects, we will proceed in a second phase of the study to evaluate the effects of gammaCore on RP associated with Scleroderma.

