## The Specific Sequential Aims of this application are as follows:

- Aim 1: Evaluate the clinical efficacy of gammaCore (16 subjects) vs sham device (16 subjects) in preventing vasospasm in 32 PRP subjects.
- Aim 2: Evaluate the clinical efficacy of gammaCore (16 subjects) vs sham device (16 subjects each) on Raynaud's symptoms and chronic PRP in 32 subjects with chronic PRP for four weeks using Raynaud's condition score.
- Aim 3: Observe response rates in an open label fashion after sham subjects are transitioned to gammaCore.

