## Statistical analysis.

Comparisons between absolute temperature, DDD, and DDDI between subjects and visits will be made. Mean values and standard deviations of the measurements IT end points will be determined. Sequentially, the differences in the mean values of temperature after a baseline and in response to cold challenge will be calculated and categorized as greater or less than1.2-fold change from the baseline average. Also, we will measure absolute temperature, DDD, and DDDI across the 2nd-4th digits bilaterally. We will calculate the mean of all absolute temperatures, DDD, and DDDI values and rate of change, and use t-test to calculate P value. P value <0.05 will be considered statistically significant. We will use one-way ANOVA for the means will be used for statistical analysis. Statistical significance will be considered if P < 0.05.

Anticipated results and interpretation. We predict that these experiments will provide the first clinical evidence that nVNS with gammaCore may be an effective treatment in PRP, by demonstrating that the stimulation abrogates vasospasm that is classically induced by cold challenge in subjects with PRP.

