## Potential pitfalls and contingency plan.

Should we be unable to detect significant changes in temperature in the digits after gammaCore vagal stimulation, we will consider using gammaCore vagal stimulation at different time intervals. Also, to eliminate effects of seasonal variability on RP, we will recruit all subjects for this study in the same season. To avoid effect of environment temperature variability on evaluation of blood flow in the digits, we will perform the testing at standard room temperature (23°C + 0.5°C).

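### Aim 1 has a fixed contrast but no named primary measure, visit or summary; if any one P < 0.05 may count, the false-positive chance exceeds 5%

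*Combined protocol and SAP*

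**What the plan says.** The first specific aim sets gammaCore (16 subjects) against sham (16 subjects) "in preventing vasospasm in 32 PRP subjects". That fixes the contrast but names no outcome variable.

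The Statistical analysis section supplies the testing rules:

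- The scope is "Comparisons between absolute temperature, DDD, and DDDI between subjects and visits will be made".
- The tested quantities are averages and a rate of change: "We will calculate the mean of all absolute temperatures, DDD, and DDDI values and rate of change, and use t-test to calculate P value".
- The threshold is "P value <0.05 will be considered statistically significant".
- Temperature differences are also "categorized as greater or less than1.2-fold change from the baseline average", with no stated role for that category.
- A second method is added: "We will use one-way ANOVA for the means will be used for statistical analysis". The 0.05 threshold is then repeated.

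The section on demonstrating the effect of treatment lists all three measures. It adds one interpretive sentence, that a high DDDI gradient points to little response. It does not make DDDI primary or attach a test to it. The DDD and DDDI cut-offs in the Thermography section are screening criteria. The Raynaud's condition score is named only for Aim 2.

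**The concern.** A 5% threshold describes the error of one test. It describes the error of the conclusion only if the plan says which test settles it, or how several tests combine. Here at least three averaged measures, and one or more rates of change, can each be declared significant. Two sham-controlled cold challenges (Week 0 and Week 4) are available, and nothing says which result decides Aim 1.

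At stake is the claim that the Statistical analysis section anticipates: first clinical evidence that the device may be an effective treatment. If that claim may rest on whichever result falls below 0.05, it carries more than a 5% risk of being made when there is no effect. Once results by arm are known, a choice of measure and visit can no longer count as pre-specified.

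**Working it through.** **Inputs from the documents.** 16 per arm, 1:1 (Study population; Aim 1). Threshold 0.05 per result, sidedness not stated. Three measures plus rate of change (Statistical analysis). The plan gives no overall error rate to reproduce. The only benchmark is one named test at 0.05: 5% in total, 2.5% in favour of gammaCore.

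**Assumptions.** Two-sided two-sample t-tests with 30 degrees of freedom, no true effect, one visit, and any single P < 0.05 counts. The documents give no correlations between measures, so a range is shown. Rate of change is counted either once (four tests) or once per measure (six tests), because the text allows both.

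**Step 1, independent tests.** Chance of at least one false positive = 1 − 0.95^k.

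- k = 3: 1 − 0.857 = 14.3%
- k = 4: 1 − 0.815 = 18.5%
- k = 6: 1 − 0.735 = 26.5%

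All three measures come from the same images, so these are upper bounds rather than likely values.

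**Step 2, three averaged measures, correlated.** Simulation, 400,000 replicates, equal correlation between measures:

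| Correlation | Any P < 0.05 | Any favouring gammaCore | All three significant, same direction |
|---|---|---|---|
| 0 | 14.3% | 7.4% | 0.0% |
| 0.5 | 12.7% | 6.4% | 0.3% |
| 0.9 | 8.5% | 4.2% | 2.2% |
| 0.99 | 6.1% | 3.0% | 4.0% |

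Repeat runs at correlation 0.5 gave 12.4% to 12.7%. The rate returns to 5% only at a correlation of 1.

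**Step 3, adding rate of change.** Measure correlation 0.5 or 0.9, crossed with mean-to-slope correlation 0 or 0.9; any P < 0.05:

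| Tests | Slope 0, measures 0.5 | Slope 0, measures 0.9 | Slope 0.9, measures 0.5 | Slope 0.9, measures 0.9 |
|---|---|---|---|---|
| Three means + one rate (4) | 17.2% | 13.1% | 14.4% | 10.0% |
| Three means + three rates (6) | 23.9% | 16.3% | 17.5% | 11.7% |

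For six tests, the part favouring gammaCore is 12.4%, 8.3%, 8.8% and 5.9% in the same order.

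**Step 4, does the ANOVA help?** For the two-arm contrast, one-way ANOVA is the pooled t-test (F = t²), so it adds nothing and protects nothing. Applied across several groups or visits, it could act as an overall test within one measure, but it gives no control across measures.

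**Step 5, what one test can detect.** The normal approximation gives a standardised difference of √(2/16) × (1.960 + 0.842) = 0.354 × 2.802 = 0.99 for 80% power. With the t distribution it is 1.02. Testing three measures at 0.05/3 = 0.0167 instead would raise it to 1.20.

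**The case against.** The strongest reply is that this is a first proof-of-concept study, that the measures overlap heavily, and that the anticipated claim is hedged. Much of that stands. High correlation shrinks the excess, to about 6% at 0.99, and the hedging lowers the cost of an error. Neither supplies the missing rule, and the plan still declares statistical significance. The excess is also conditional: requiring all three averaged measures to agree would bring the rate below 5%, but the plan does not say that either.

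A reader might infer three stronger points that the documents do not support.

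- **That every time point and region is tested separately.** Three measures at five post-challenge times would make 15 tests per visit. The visit descriptions do generate those values, but the t-test sentence concerns averages and rate of change. No test of each time or region is planned, so no error rate is claimed for that reading.
- **That the Abstract and the contingency plan contradict each other.** The contingency begins "Should we be unable to detect significant changes in temperature in the digits after gammaCore vagal stimulation", and the Abstract says "If successful in demonstrating measurable local vasodilatory effects, we will proceed in a second phase of the study". A conflict would require temperature in the digits to exclude DDD, yet the Thermography section gives the DDD threshold in °C. It would also require the go-ahead to depend on P < 0.05, which the Abstract does not state.
- **That the plan has no comparison at all.** Aim 1 fixes gammaCore against sham, the Week 4 description ends the sham-controlled period, and Aim 2 has its own named score. What is missing is the measure, the visit, the summary over time and the decision rule.

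**Conclusion.** The point holds in conditional form. The plan sets an unadjusted 0.05 threshold for several results bearing on Aim 1 and does not say which one, or how many, decide it. If any one may count, the error exceeds 5% for every number of tests from three upward and every correlation below 1. That direction is firm.

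The size is illustrative because the correlations are assumed: about 8.5% to 12.7% for the three averaged measures at one visit, and about 12% to 24% with a rate-of-change test for each measure. On the averaged measures, the excess in favour of gammaCore is modest: about 4% to 6% against 2.5%. Given the proof-of-concept setting, this should be corrected before analysis, but it does not undermine the trial.

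**What to change.** Before results by arm are seen, name one primary between-arm comparison for Aim 1 at two-sided 0.05. The choice of measure belongs to the investigators. Examples are DDDI or absolute digit temperature, averaged over digits 2 to 4 of both hands and over the post-challenge times at the Week 4 challenge, the end of the sham-controlled period. The chosen measure must be defined in full; the documents give no formula for DDDI, so choosing it means adding one.

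Report the other thermography measures, times, regions, rate of change, the 1.2-fold category and the other visits as secondary or exploratory, with estimates and 95% confidence intervals. Aim 2's Raynaud's condition score stays a separate aim.

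If the investigators prefer no primary test, label every comparison exploratory and remove both the significance declaration and the efficacy wording.

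The cost is analysis-plan wording, with no new data. Efficacy could no longer be claimed from whichever result looks best. A single test at 16 per arm has 80% power only for a standardised difference of about 1.02, a limit that the sample size already sets.

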#### D. APPROACH and METHODOLOGY

# 1. Assessment of digital blood flow in response to cold challenge test

We used FLIR thermography system (Wilsonville, OR) to evaluate blood flow in the digits in response to cold challenge test. The advantage of IT is that we can obtain dynamic assessment of blood flow in the hands as reflected by change in temperature in response to cold challenge tests, as well as the ability to obtain single point measurements. **Figure 2** shows dynamic changes in surrogate marker of blood flow as detected by thermal images during the three phases of active Raynaud's phenomena that we were able to reproduce by cold challenge test.

**Figure 2:** An illustrative example of dynamic changes in vascular perfusion that are detected by infrared thermography. A) Active vasospasm, B) spontaneous improvement in blood flow, C) Hyperemia. Blue-yellow regions indicate areas of lower perfusion compared to red regions.

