# Thermography

We will use FLIR system to measure temperature and blood flow at the digits. After the cold challenge, subjects will place their hands on a setup of a carpet square measuring a length of 42.5 cm by 29.5 cm wide, placed backing side up (to reduce reflection), on a table with a grate resting on the carpet where the subject will be instructed to rest hands on. We will use 2 thresholds for use as screening when subjects do the first cold challenge without neurostimulation:

- 1. A Distal Dorsal Difference (DDD) >1°C at base line or
- 2. DDDI should > 20% at 5 min after the cold stress.

Subjects who meet the screening threshold of clinically meaningful change from baseline on the initial cold challenge will be enrolled into the study.

Week -4 (Screening). The screening visit where eligibility testing will be performed utilizing the cold challenge test, a baseline image will be taken, and physician verbal history interview performed. Subjects will begin to keep a diary of Raynaud's symptoms and number of attacks. Throughout the study, the diary will be collected at week 0, 4, 8, and 12. A diary will be provided at week -4, 0, 4, and 8. Beginning at week 0, stimulation time and occurrences with gammaCore device will be recorded in the diary along with at week 4. There is no use of gammaCore or sham at this point. Subjects continue their current standard of care treatments, except for medications prohibited while enrolled in the study.

Week 0 (Randomization). The first 32 subjects that meet screening criteria will be enrolled into the study. Diaries from Week -4 to Week 0 will be collected, and a new diary given. The 32 subjects will be randomized 1:1 to either sham device (16) or gammaCore device (16). At week 0 subjects will have a follow up image #1 taken and then be treated with sham or gammaCore -20 minutes prior to cold challenge. The first set of stimulation begins at -20 minutes (2 minutes on each side of the neck for a total of 4 minutes) and then at -4 minutes the second set of stimulation occurs (2 minutes on each side of the neck for a total of 4 minutes)

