performed by the subject, monitored by the investigator, or delegated study personnel immediately after cold challenge. Using FLIR thermography to measure absolute temperature, DDD, and DDDI will be calculated from images of both hands taken at baseline, obtained by a video where images are captured at 1 min, 5 min, 10 min, 15 min and 20 minutes after the cold challenge will be measured at the dorsum and digits 2nd-4th. Images measuring the absolute temperature, DDD, and DDDI at specific regions as well as the average of all regions will be generated as a surrogate marker of blood flow.

Prior to cold challenge subjects will be trained on proper usage and administration of sham and gammaCore devices. Subjects will stimulate for 4 minutes (2 minutes each side of neck) twice a day, once in AM and once in the PM, at least 8 hours apart\_for a total of 8 minutes of stimulation daily. Subjects will begin to log the completion of stimulation and occurrences with the device, and continue recording Raynaud's symptoms and number of attacks in the diary. Subjects will continue on their current treatments with sham or gammaCore device, and continue to refrain from medications prohibited while enrolled in the study.

Week 1. Subjects will return for observation of administration of treatment with any correction if necessary and confirm that subject is documenting RP symptoms and number of attacks as well as the use of the device in the diary.

Week 2. Subjects will be contacted via telephone for a follow up call to address any device stimulation issues, make corrections if necessary, as well as confirm that subject is documenting RP symptoms and number of attacks as well as the use of the device in the diary.

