Week 4 (Open Label). Subjects will return for cold challenge test and bring device back with them. Subjects will have follow up image #2 taken and then be treated with their current sham or gammaCore -20 minutes prior to cold challenge (stimulation 2 minutes each side of the neck for a total of 4 minutes) and then at time -4 minutes (stimulation 2 minutes each side of the neck for a total of 4 minutes) performed by the subject and monitored by the investigator, or delegated study personnel) immediately before cold challenge. Using FLIR thermography to measure absolute temperature, DDD, and DDDI will be calculated from images of both hands taken at baseline, obtained by a video where images are captured at 1 min, 5 min, 10 min, 15 min and 20 minutes after cold challenge will be measured at the dorsum and digits 2nd-4th. Images measuring the absolute temperature, DDD, and DDDI at specific regions as well as the average of all regions will be generated as a surrogate marker of blood flow.

Following Week 4 cold challenge sham subjects will be placed on active treatment with gammaCore so that all subjects will be on open label active treatment at Week 4. All subjects will be retrained on proper usage and administration of gammaCore. Subjects will stimulate for 4 minutes (2 minutes each side of neck) twice a day, once in AM and once in the PM at least 8 hours apart, for a total of 8 minutes of stimulation daily. The diary from week 0 to 4 will be collected and subjects will be provided a new diary to continue recording the completion of stimulation and occurrences with the device, and Raynaud's symptoms and attacks. Subjects will continue their treatments with the gammaCore device and continue to refrain from medications prohibited while enrolled in the study.

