## Demonstrating the effect of treatment in response to cold challenge.

We will calculate absolute temperature, DDD, and DDDI from images of both hands taken at baseline, 1 min, 5 min, 10 min, 15 min and 20 minutes after cold challenge at the dorsum and digits 2nd-4th. High gradient of DDDI indicates insignificant response of the treatment modality.

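### The t-tested mean is not limited to post-challenge readings, so taken literally it includes an image taken before that visit's stimulation

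*Combined protocol and SAP*

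**What the plan says.** The Statistical analysis section defines the tested quantity in one sentence: "We will calculate the mean of all absolute temperatures, DDD, and DDDI values and rate of change, and use t-test to calculate P value". It names no visit, time point or window, and does not say what *all* ranges over.

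The section just before it, on demonstrating the effect of treatment, says the same three measures are calculated from "images of both hands taken at baseline, 1 min, 5 min, 10 min, 15 min and 20 minutes after cold challenge". That is six readings per challenge, one of them the baseline.

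The visit descriptions under Thermography give the order of events. For Week 0: "At week 0 subjects will have a follow up image #1 taken and then be treated with sham or gammaCore". For Week 4: "Subjects will have follow up image #2 taken and then be treated with their current sham or gammaCore". Week 8 follows the same order. The plan does not say in so many words that this follow-up image is the baseline reading, but it is the only image described before the challenge at these visits.

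Two passages point to another meaning of *all*. The sentence before the t-test sentence begins "Also, we will measure absolute temperature, DDD, and DDDI across the" and goes on to digits 2 to 4 on both sides. The visit descriptions also plan images "at specific regions as well as the average of all regions will be generated as a surrogate marker of blood flow".

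**The concern.** Aim 1 asks whether gammaCore prevents cold-induced vasospasm. A reading taken before the day's stimulation and before the cold cannot show that. At Week 0 no device has yet been used, so randomisation makes the expected arm difference in that image zero. If it supplies one sixth of the tested mean, it shrinks the effect by one sixth and does little to reduce the noise.

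The trial has 16 subjects per arm, and the sample-size statement gives no power, effect size or standard deviation, so the plan shows no margin to absorb such a loss. Leaving *all* undefined also means the averaging rule could be chosen after the data are seen.

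**Working it through.** **The plan's own figure.** Study population justifies 32 subjects by 90% confidence and a 10% margin of error. The usual precision formula for a proportion, with p = 0.5, gives 1.645² × 0.25 / 0.10² = 67.6, so 68. With a finite population equal to the 40 consented it gives 25.4, so 26. Neither is 32, and neither is a power calculation, so power has to be worked out from assumptions.

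**Inputs from the document.** Six readings per challenge; 16 per arm; significance at 0.05.

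**Assumptions.** Two-sided test (the plan does not say); equal variance at each reading; a common correlation r between readings, taken from 0.3 to 0.9; the same effect at 1, 5, 10, 15 and 20 minutes; zero effect on the pre-stimulation image (Week 0).

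**Step 1, effect.** If the effect is δ at each post-challenge reading, the mean of those five has effect δ. The mean of all six has effect 5δ/6 = 0.83δ.

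**Step 2, variance.** In units of the single-reading variance, a mean of k readings has variance (1 + (k − 1)r)/k. For five readings this is (1 + 4r)/5; for six it is (1 + 5r)/6.

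**Step 3, ratio of standardised effects**, six readings against five: (5/6) × √{[(1 + 4r)/5] / [(1 + 5r)/6]}.

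**Step 4, power.** By the noncentral t distribution with 30 degrees of freedom, 80% power at 16 per arm needs a standardised effect of 1.024. Multiply this by the ratio and recompute.

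| r | variance, 5 | variance, 6 | ratio | ratio² | power (from 80%) |
|---|---|---|---|---|---|
| 0.3 | 0.440 | 0.417 | 0.856 | 0.733 | 67% |
| 0.5 | 0.600 | 0.583 | 0.845 | 0.714 | 66% |
| 0.7 | 0.760 | 0.750 | 0.839 | 0.704 | 65% |
| 0.9 | 0.920 | 0.917 | 0.835 | 0.697 | 65% |

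The squared ratio is the share of the sample that remains effective, so the Week 0 loss is like giving up 27% to 30% of subjects.

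**Step 5, a fixed effect.** With an effect of 1 SD at every post-challenge reading and r = 0.5, the six-reading mean has standardised effect 0.833/√0.583 = 1.09 and power 85%. The five-reading mean has 1/√0.600 = 1.29 and 94%.

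**Step 6, Week 4.** Suppose the image before that day's stimulation carries a fraction f of the effect, from four weeks of daily use. The factor 5/6 becomes (5 + f)/6. At f = 0.5 the ratio is 0.94 to 0.92 and 80% power becomes 75% to 73%. At f = 1 the ratio is 1.03 to 1.00 and nothing is lost. The document gives no value for f.

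**Step 7, use as a covariate.** Adjusting the five-reading mean for a pre-stimulation reading that has correlation r with each of the five reduces its variance by r². At r = 0.5 that is 0.600 − 0.250 = 0.350, so the standardised effect in Step 5 rises from 1.29 to 1/√0.350 = 1.69.

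**The case against.** The strongest objection is that *all* need not mean all times. The neighbouring sentence is about digits, and the visit descriptions plan an average over regions. On that reading there is no dilution. This stands as a reading of the text, but it leaves the time point entering the t-test wholly unspecified, and the same rewording is needed.

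The pooled mean is also not the only quantity in the section. The sentence covers a rate of change, and the section separately compares baseline with the cold response (categorised at a 1.2-fold change) and plans a one-way ANOVA. This is true, but none of these is named as the deciding analysis, so none settles what the t-test uses.

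Averaging over time also reduces noise. In the Step 5 example the six-reading mean, at 85%, beats a single 5-minute value, at 78%. That argues for averaging the post-challenge readings, not for including the pre-stimulation image.

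A reader might go further and infer that late hyperaemia makes sham hands the warmer ones and so cancels an early benefit. The document does not support this. It lists the phases as "A) Active vasospasm, B) spontaneous improvement in blood flow, C) Hyperemia" in an illustrative figure, gives no minutes for them, and does not say that hyperaemia differs by arm. A reader might likewise prefer a 5-minute or 1-to-10-minute outcome. The 5-minute value appears only as a screening threshold, and an early window can lose power. Take assumed effects of 0, 0.5, 1, 2, 2 and 2 °C at the six readings, SD 2 °C and r = 0.5. Power is then 28% at 5 minutes and 50% for the 1-to-10-minute mean, against 61% for all six readings. The mean of the five post-challenge readings has effect 7.5/5 = 1.5 °C, SD 2 × √0.600 = 1.55 °C and power 75%.

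**Conclusion.** The point holds in a limited form. The tested summary is undefined and, taken literally, mixes a pre-stimulation image into the outcome. At Week 0 this multiplies the standardised effect by 0.86 to 0.83 and takes 80% power to about 67% to 65%.

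These figures rest on a constant effect from 1 to 20 minutes, equal variances, a common correlation of 0.3 to 0.9, a two-sided test, and the inference that the follow-up image is the baseline reading. The zero arm difference is assured only at Week 0. At Week 4 the loss may be smaller, and it vanishes if the image already carries the full effect. No conclusion is drawn about cancellation by hyperaemia or about the best window, because the document does not time the phases. This is a free improvement rather than a flaw that invalidates the trial.

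**What to change.** In Statistical analysis, replace the mean of all values by the following rule, applied to each measure:

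- One value per subject per visit, averaged over digits 2 to 4 of both hands and over the readings at 1, 5, 10, 15 and 20 minutes after the challenge.
- The pre-stimulation image is kept out of the outcome and used as a covariate. At Week 4, use the Week 0 pre-stimulation image, because adjusting for the Week 4 image could remove part of a real effect.
- Each time point is also reported separately by arm, so that an early or a late effect can be seen.

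The cost is wording only; no visit, image or measurement is added. The trade-off is that an effect confined to a few minutes is diluted in the five-reading mean and shows mainly in the separate reports.

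Before the text is final, the Week 0 description must be reconciled with itself. It times the second stimulation at −4 minutes but also places it immediately after the cold challenge, which affects which readings follow both stimulations.

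### Visit comparisons on the same subjects are planned with a t-test of unstated pairing and one-way ANOVA, and arms are compared without baseline adjustment, so power is given up

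*Combined protocol and SAP*

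**What the plan says.** The plan for testing is the Statistical analysis section of the combined protocol and SAP. Its scope is "Comparisons between absolute temperature, DDD, and DDDI between subjects and visits will be made". Two methods are named, each at P<0.05. The first is "We will calculate the mean of all absolute temperatures, DDD, and DDDI values and rate of change, and use t-test to calculate P value". The second is "We will use one-way ANOVA for the means will be used for statistical analysis". The section does not say whether the t-test is paired, what the ANOVA factor is, or which test answers which comparison.

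Baseline appears in three ways: a difference between baseline and post-challenge temperature, a rate of change, and a category, "categorized as greater or less than1.2-fold change from the baseline average". None is a covariate in an arm comparison, and no test is named for the category.

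Under Thermography, the same subjects have cold challenges at Weeks -4, 0, 4 and 8. From Week 0 each has images at baseline and at 1, 5, 10, 15 and 20 minutes, and "Images measuring the absolute temperature, DDD, and DDDI at specific regions as well as the average of all regions will be generated". After the Week 4 challenge "sham subjects will be placed on active treatment with gammaCore so that all subjects will be on open label active treatment".

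Pre-treatment values are available. The Week -4 challenge is done without stimulation, and one of its two alternative entry criteria is "DDDI should > 20% at 5 min after the cold stress". At the next visit, "At week 0 subjects will have a follow up image #1 taken and then be treated with sham or gammaCore".

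**The concern.** Values from one person at different visits are normally positively correlated. Ordinary one-way ANOVA and the two-sample t-test treat them as coming from different people, so the stable differences between people stay in the error term. A real change from one visit to another can then be missed. The arm comparison has a related, milder weakness: an unstimulated pre-treatment challenge is collected but not used to reduce unexplained variation.

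With only 16 subjects per arm, neither loss is easily absorbed. The Potential pitfalls section would consider other stimulation intervals if no significant temperature change is found, so a missed effect would influence what is done next.

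**Working it through.** **The plan's own figure.** There is no power figure to reproduce. The Study population section bases the sample size on 90% confidence and a 10% margin of error. Read as a precision formula with an assumed proportion of 0.5, that gives 1.645² × 0.25 / 0.10² = 67.6, or 68, not 32. This contains no effect size or SD, so it does not enter the check below.

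**Inputs.** From the documents: 16 subjects per arm, 32 in all, and a significance level of 0.05 (two-sided is assumed, since sidedness is not stated). Not in the documents and therefore assumed: within-subject correlation ρ of 0.3, 0.5 or 0.7, equal for all pairs of visits; a 0.8 SD shift between visits; normal data; no dropout. Triples below follow that order of ρ.

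**Step 1: two visits, n = 16, one value per subject and visit.**
- The true variance of the difference in visit means is 2σ²(1−ρ)/n. The unpaired test uses 2σ²/n.
- The true standard error is therefore √(1−ρ) = 0.84/0.71/0.55 of the one used, and the test is conservative.
- Simulated type I error, unpaired: about 2%/0.8%/0.1%. Paired: about 5% throughout.
- Simulated power at 0.8 SD, unpaired: about 61/63/65%.
- Paired, by noncentral t with 15 df: noncentrality is 0.8 × √(16/[2(1−ρ)]) = 2.70/3.20/4.13 against a critical value of 2.131. Power is 71.5/84.8/97.1%, in line with the simulated 71/85/97%.

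**Step 2: more than two visits.** Ordinary one-way ANOVA over three visits has a simulated type I error of about 1.5–1.7%, 0.4–0.5% and 0.02–0.04%. With four visits in one arm of 16 and a 0.8 SD shift at one visit, its power is 58/55/53%, against 77/90/99% for a repeated-measures analysis.

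**Step 3: sham versus gammaCore, 16 per arm, one mean per subject.**
- The two-sample t-test holds 5%. With 30 df, the difference detectable with 80% power is 1.02 SD.
- ANCOVA multiplies the residual SD by √(1−ρ²) = 0.954/0.866/0.714 and uses 29 df, where the unadjusted detectable difference is 1.025 SD. The result is 1.025 × these factors = 0.98/0.89/0.73 SD.
- Screening narrows the Week -4 values and weakens the correlation. Assuming 60–80% of screened subjects pass (32 of 40 consented would be 80%), ρ falls to 0.24–0.27/0.42–0.46/0.61–0.66. The detectable difference becomes about 0.99/0.91–0.93/0.77–0.81 SD.

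**The case against.** **This is underspecification, not a stated wrong method.** The t-test may be meant as paired, and one-way ANOVA may be loose wording for a repeated-measures analysis. That stands: the power loss arises only under the unpaired reading. But nothing in the document selects the other reading, and one-way ANOVA as normally understood has no subject term.

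**Unpaired testing between visits errs on the safe side.** This also stands. The risk in these comparisons is a missed change, not a false claim.

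**ANCOVA is an efficiency preference.** Leaving it out does not bias a randomised comparison, and at a correlation of 0.3 it gains little. That limits its weight, but the covariate comes from a challenge already being done.

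**A reader might infer inflated false positives.** If six digit values per subject entered an arm t-test as independent, the error rate would be 22–36% at the assumed correlations. No section plans this. The references to a mean of all values and to an average over regions point to averaging, which keeps 5%.

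**A reader might also count many arm tests, or assume that the 1.2-fold category will be tested.** No primary measure is named, and that is worth correcting. But any count of tests, and any test of the category, would be the reader's own: the plan lists neither.

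**Conclusion.** The point holds as a loss of power that can be avoided with data already collected. For visit comparisons, ignoring pairing costs about 10, 22 or 32 percentage points of power (71−61, 85−63, 97−65) with 16 subjects and a 0.8 SD shift. For the arm comparison, ANCOVA lowers the detectable difference by 0.04 to 0.29 SD before allowing for screening, and by less after it. These sizes rest on assumed correlations and effect sizes; the pattern (conservative unpaired tests, more power when paired) needs only positive correlation between visits.

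It would go too far to conclude that the randomised comparison is invalid. On one mean per subject it is not.

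One inconsistency limits which visit can be primary. The Week 0 text under Thermography times the two stimulation sets at −20 and −4 minutes relative to the challenge, then describes stimulation as immediately following the challenge. The Week 4 text places it immediately before.

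**What to change.** In the Statistical analysis section:

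1. For visit comparisons, replace one-way ANOVA with a paired t-test (two visits) or a mixed model with a random subject effect (more than two).
2. Analyse one value per subject and visit: the average over digits 2–4 of both hands at one named time. This also rules out treating digits or times as independent. Name one primary measure at Week 4, for example 5-minute DDDI, and label the rest supportive.
3. Compare arms at that visit by ANCOVA on the unstimulated Week -4 value of the same measure.
4. Limit randomised arm comparisons to visits before the switch. Report Week 4 to Week 8 as a paired, non-randomised within-subject change. Aim 3 only asks to observe response rates, so testing means there is optional.

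Reconcile the Week 0 statements on stimulation timing before that visit is used as primary or modelled together with Week 4.

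The cost is analysis wording, slightly more analysis work, and keeping the Week -4 5-minute value for every enrolled subject, including those who qualify on baseline DDD alone. No new visits or images are needed.
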